Additionally to the statistical analysis, it presents an evaluation checklist associated to T8.5, that provides the fundamentals for the non-clinical (i.e., technical) evaluation of the RETENTION solution (i.e., the RETENTION Patient Edge instances – Edge or mobile app, the RETENTION Clinical Site Backend - CSB, and the RETENTION Global Insights Cloud – GIC), along with associated testing activities scheduled to be performed to validate the solution in terms of performance and indented usage. To this extent, usability of interaction elements (CSB-GIS Dashboards, mobile app interface) will be measured by monitoring end-users' performance on a given set of important tasks to certify that those met the end-users needs, while technical indicators associated with the execution of the functional and non-functional requirements and the overall performance of the solution. The first and complete version of this evaluation framework will be presented in the forthcoming D8.4.

2 About this Document

Role of the deliverable

The role of this deliverable is to present the protocol that includes the study design, primary and secondary endpoints, relevant guidance documents, regulatory status and activities, the subjects/population of this study with a definition of sub-population if subgroup analysis is intended, the Inclusion and the exclusion criteria, the statistical analysis with the plan and the power calculation, the cumulative safety and efficacy information, the description of recruitment strategy, the description and the assignment of interventions and notifications and the study management, study monitoring, data and sample management. The Evaluation Framework, a tool used for associating relationships between the work to be performed in T8.5 and the rest of the project, establishes a range of methods and tasks appropriate for the purpose to establish primary evaluation targets and process.

Relationship to other RETENTION deliverables

This deliverable is related with most of the deliverables but more closely with D10.1-10.4, D5.1, D5.2, D1.1, D3.1, D3.2, D4.1, D4.2, D8.1 and D8.3-D8.6.

Structure of the document

The current deliverable provides the protocol of the RETENTION system.

The deliverable includes 4 sections and the Appendix. Thus, the structure of the D8.2 is as follows:

- Section 1: presents the executive summary
- Section 2: presents the purpose, scope, structure of this deliverable and the relation to the other deliverables
- Section 3: presents the protocol
- Section 4: presents the first version of the evaluation framework

3 Clinical study

3.1 Study Identifier

The full name of the study is: HEART FAILURE PATIENT MANAGEMENT AND INTERVENTIONS USING CONTINUOUS PATIENT MONITORING OUTSIDE HOSPITALS AND REAL-WORLD DATA. The study identifier is RETENTION.

3.2 Study design and endpoints

3.2.1 Study design

The aim of this study is to investigate the effect of introducing daily and environmentally aware patient monitoring protocols outside hospitals and interventions informed by it, on all-cause and cardiovascular mortality, heart failure hospitalisations or emergency room visits, and quality of life in patients with symptomatic chronic heart failure (HF), patients with implanted Left Ventricular Assist Device (VAD) and heart transplant (HT) recipients.

Patient specific measures related to the vitals (including weight, blood pressure, heart rate, peripheral capillary oxygen saturation), daily physical activity, quality of sleep (as expressed through heart rate variability), psychological state and nutrition intake will be collected. In addition, the study will collect real world data derived from non-medical sources regarding environmental factors in the living environment of patients participating in the study (i.e., ambient temperature, relative humidity, pollutants).

The data will be collected through a Randomised Clinical Trial (RCT) where the aforementioned groups of patients, between 18 and 75 years of age, will be observed in an outpatient setting through the remote monitoring platform of RETENTION, which will be created for this purpose, and the standard clinical practice. A total of 450 participants will be recruited to participate in the study. 30-35% of the recruited patients will be women. This is because up until now, women have been underrepresented in most heart failure clinical trials, despite the fact that disease prevalence remains generally the same between both sexes. When it comes in heart failure with reduced ejection fraction, subgroup analysis of several trials reveals that women were older, more likely to have pre-existing hypertension and less likely to have coronary artery disease. In addition, despite heavier symptom burden, women fared better in survival and hospitalisation risk. LVAD implantation has also been studied mainly on male patients with the added restriction of smaller ventricular dimensions rendering device support unavailable in women.

A control group of patients of similar age dispersion will also be set up and followed up only by the standard means and procedures currently employed as best practices. This will be a multi-centre RCT conducted at six clinical centres in Greece, Italy, Germany and Spain.

Randomisation: A total of 450 participants will be recruited to participate in the study, all of whom are treated according to standard heart failure care protocols. All patients will be provided with monitoring devices and home sensors to collect the data required by the study. Data will be collected continuously from all the participants. Half of the participants (Test group, n=225)data, collected through the provided devices, will be made available to treating physicians for review and additional interventions as determined by the analysis of these data may be done according to the judgement of the treating physician. In the rest of the participants (control group, n=225), treating physicians will be blinded to the data collected through the RETENTION platform and therefore no additional interventions will be done. Randomisation will be conducted centrally. Randomisation will be conducted centrally through the RETENTION platform.

Randomisation will be stratified by centre and type of patients (heart failure, LVAD and heart transplant) with a block size of 4.

Duration¹: It is re-estimated that instead of eight (8), fourteen(14) months will be required to collect all the essential documents from all participating sites, prepare the files for submission to Ethics and Regulatory authorities in all four countries in order to obtain the appropriate approvals later on, by M20, instead of M18 that was originally planned. Upon receipt of ethics approvals from all sites, sites will be activated within one (1) month. Patient recruitment will start in month 20 of the project and will last for ten (10) months. Following recruitment and randomisation, each participant will be monitored in an outpatient setting through the remote monitoring platform of RETENTION for a period of 18 months. Over this period, each participant will have regular follow ups with clinic visits (upon registration/randomisation, and at months4,8,12 and 18) in addition to the clinic visits required by the standard heart failure management protocols. All clinic visits can be performed within ±15 days from the expected date. Upon completion of patient monitoring period, three (3) months will be needed for activities related to the termination of the study (e.g., for final analysis of the data collected by the study).

Equipment and means of data collection: The RCT will be conducted based on the use of non-medical equipment including monitoring devices (e.g., smartphone, weight Scale, smartwatch, blood pressure monitor, oximeter, home sensors) that will be provided to the study participants (patients) of both the test and the control group by the project. The smart devices will be used for running the clinical study application (RETENTION smart application), during which they will generate patients-associated usage data (measurements) and data provided by patients (via questionnaires), later on to be transmitted, aggregated and analysed (see Sect 3.7.3 below). All the devices that will be handed to the patients will be set up and tested prior to the hand over to them. They will also receive the basic training required for using these devices.

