3.4 Subjects / Population(s)

3.4.1 Definition of sub-populations if subgroup analysis is intended

There will be two groups of patients. The first group will be subject to remote monitoring through the RETENTION platform but no additional intervention will be given other than the standard follow-up practice as it has been performed in the participating clinical centres during the last decade. The second group will be monitored and followed up on using the remote monitoring platform, and additional interventions will be provided as the system evolves with time based on the data analytics. All participants will take part in the clinical study after detailed explanation of the project's aims and their participation requirements. They will receive an information leaflet and will sign an informed consent form. They will be able to leave the clinical study at any point without any kind of explanation necessary. All participants will be assessed at baseline, and at months 4,8,12 and 18.

A total of 450 patients across the six hospitals will participate in the project. These patients will include:

- 200 patients with HF not enlisted for transplant at the time of their recruitment (approximately 44% of the total number of patients)
- 150 LVAD patients (approximately 34% of the total number of patients)

100 heart transplant recipients (approximately 22% of the total number of patients)

Of these patients 225 patients will be the test group, referred to as remote patient monitoring and interventions group (RPMI group), and 225 patients will be the control group, referred to as remote patient monitoring and usual care (RPMUC group). The control and the test group for each site will have equal numbers of recruits in each of the above three categories of patients. Of the recruited patients 30-35% will be women. This is because up until now, women have been underrepresented in most heart failure clinical trials, despite the fact that the disease prevalence remains generally the same between both sexes. The individual clinical units which will participate in the study are expected to recruit the numbers of patient shown in Table 1.

Table 1: Recruitment targets for individual clinical partners and countries							
Partner	Clinical Unit	No of Patients	Country				
OCSC	OCSC	100	Greece				
NKUA	NKUA	80	Greece				
UNIBO	UNIBO	100	Italy				
UKESSEN	UKESSEN	100	Germany				
SERMAS	Hospital Universitario Ramón y Cajal (SERMAS-HURC)	70	Spain				

4 5 Ta

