4.1 Phase A: Pre-recruitment

During the pre-recruitment, the Clinical team checks the participants' condition in accordance with the inclusion and exclusion criteria (defined in section 3) and assess their willingness to participate in the RETENTION study. In some cases, additional examinations for participants with a recent history of what could become exclusion criteria can be requested. Those best meeting the requirements and who could benefit from this project through remote monitoring, will be informally approached by the Pilot Clinical team to be informed about the project objectives, the involved activities, their tasks upon participation and the advantages and disadvantages according to their health condition that they could obtain.

Subsequently, those who are willing, without a shadow of a doubt, to participate (and meet the selection criteria) form a list whose members will be later contacted at the start of the recruitment procedures. The list contains personal data (i.e., full names, contact details, other PIIs, desire to participate), and will be under the supervision of the head of the Pilot Clinical team. For those that have met the selection requirements and are keen to participate, still have expressed some doubts or concerns, additional explanations could be provided, and their concerns are collected for future evaluation.

The list containing personal data of potential RETENTION study participants is kept in a safe place. This information is not part of the one collected by the RETENTION platform.

Information will be erased once the pre-recruitment phase is over.

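### A single stated block size of 4 within centre and patient type would let a site team that keeps count know up to about 32% of allocations in advance; varied, undisclosed block sizes are a cheap improvement

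*Protocol*

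**What the plan says.** Section 3.2.1 (Randomisation) sets the scheme: "Randomisation will be stratified by centre and type of patients (heart failure, LVAD and heart transplant) with a block size of 4". The arms are planned at 225 each, so every block holds two test and two control places. Allocation is made centrally through the platform. Nothing says that the block size varies or is kept from sites, and Section 3.3 reports that all sites approved the protocol.

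Section 3.2.1 also describes how the arms differ. Test-group data "will be made available to treating physicians for review and additional interventions", while physicians are blinded to the platform data of controls. Section 3.7.5 adds that notifications are generated in both arms but reach clinicians only for the intervention arm. The blinding therefore covers the controls' data, not which arm a patient is in.

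Section 4 makes one site clinical team responsible for recruitment, protocol adherence and monitoring. Under Section 4.2 that team phones listed candidates, sets their appointments, confirms eligibility and obtains consent, and all its members can open the full record of each recruit at their site.

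On balance, Section 3.4.1 states: "The control and the test group for each site will have equal numbers of recruits in each of the above three categories of patients".

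**The concern.** Central allocation hides the list. It does not hide what has already been allocated. With a constant, known block size, past allocations are enough to work out some future ones: in a 2+2 block the fourth is always determined, and the third is determined whenever the first two match. Here the people who can see past arms are also those who decide which listed candidate is called in next and who judge eligibility.

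If that knowledge were used, even unconsciously, to place sicker or healthier candidates into known slots, the arms would differ at entry in ways that the recorded covariates need not capture. Later analysis cannot be relied on to remove that, so it is better prevented in the randomisation settings before recruitment.

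**Working it through.** The protocol gives no figure for predictability, so there is none to reproduce.

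**Inputs.** Block size 4, 1:1, strata of centre by patient type (Section 3.2.1). "This will be a multi-centre RCT conducted at six clinical centres in Greece, Italy, Germany and Spain" (Section 3.2.1), so 6 × 3 = 18 strata averaging 450/18 = 25 patients. Type targets are 200 heart failure, 150 LVAD and 100 transplant (Section 3.4.1). Site targets are 100, 80, 100, 100 and 70, the last for the Spanish partner (Table 1).

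**Step 1: certainty in a complete block.** There are C(4,2) = 6 equally likely sequences.
- AABB and BBAA use up one arm after two patients, so the last 2 allocations are certain.
- ABAB, ABBA, BAAB and BABA make only the last 1 certain.
- Expected certain allocations per block: (2×2 + 4×1)/6 = 4/3. Share: (4/3)/4 = 33.3%.
- By position in the block: 0, 0, 1/3, 1.

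**Step 2: best guess in a complete block.** The best strategy is to guess the arm with more places left. The chance of being right by position is 1/2, 2/3, 2/3, 1, which sums to 17/6. Share: (17/6)/4 = 17/24 = 70.8%.

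**Step 3: unfinished last blocks.** A stratum of 25 is six complete blocks plus one patient.
- Certain: 6 × 4/3 = 8 per stratum; 18 × 8 = 144 of 450 = 32.0%.
- Best guess: (6 × 17/6 + 1/2)/25 = 17.5/25 = 70.0%.
- Using the Table 1 targets split 200:150:100 instead gives 144.7 of 450 (32.1%) and 70.3%. The result is the same whether the Spanish 70 is treated as one site or as two of 35.

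**Step 4: after the change.** Randomly mixed blocks were simulated in 6,000 strata of 25, against a guesser who knows the set of sizes (each equally likely) but not the size in use. Running fixed 4 through the same simulation returned the exact values from Step 3.

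| Scheme (strata of 25) | Known with certainty | Best guess correct |
|---|---|---|
| Fixed 4 | 32.0% | 70.0% |
| Random 4 and 6 | 5.7% | 68.3% |
| Random 4, 6 and 8 | 2.3% | 67.0% |

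**Step 5: possible bias, under assumed inputs only.** Bias in the mean difference = (share of patients steered) × (gap in expected days lost between those steered to each arm). About one third of slots are predictable.
- Low: 10% of predictable slots, 10-day gap: 0.10 × 1/3 × 10 = 0.3 days.
- High: one third of predictable slots, 30-day gap: 1/3 × 1/3 × 30 = 3.3 days.
- Planned difference (Section 3.5): 29 − 17 = 12 days, so the range is about 3% to 28% of it.

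Neither the steered share nor the gap comes from the documents. The 30-day gap exceeds the whole expected control mean of 29 days.

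**The case against.** A single small block with central stratified allocation is a common choice. Nothing here is miscalculated, and a small block serves the stated aim of equal arms within each site and type. Both arms receive the devices, which removes one motive for steering a patient. The 32% is an upper limit: it needs someone at every site to tally by patient type. No sentence says that recruiters are told the block size; that is inferred from its place in a protocol that all sites approved. All of this stands. It makes the point an improvement rather than an error, but it does not remove the opportunity.

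Some stronger readings are tempting and are not supported:
- A reader might infer a bias of about 3 days. That needs the high inputs above, with steering in the same direction across centres and patient types. The documents give no basis for choosing it over 0.3 days or none.
- A reader might take Section 4.1 as proof of steering, since it says "Those best meeting the requirements and who could benefit from this project through remote monitoring, will be informally approached by the Pilot Clinical team". That step is pre-recruitment: it builds a list of people to be contacted once recruitment starts, so as written no allocations yet exist to learn from. The relevant discretion is the order of calls and appointments in Section 4.2, which is narrower.
- A reader might expect mixed blocks to end guessing. They remove most of the certainty but little of the guessing advantage (70% to 68%).
- A reader might think that locking a patient's eligibility and baseline data before releasing the allocation would cure this. It would not, because the prediction is made before that patient is chosen. Section 4.2 already has eligibility confirmed and consent signed before the platform record is created.

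The reply that randomisation is central does not meet the point, because prediction uses past allocations and not the list.

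**Conclusion.** The point holds as a cheap improvement. With one stated block size of 4, arms visible after randomisation, and one team that recruits, schedules and monitors, up to about 32% of allocations (about 144 of 450; 33.3% in complete blocks) could be known in advance and about 70% guessed correctly. This assumes that the size is constant as written, that site teams know it, and that they keep count within patient type. The documents establish that selective entry is possible. They do not show that it would happen, and the size of any resulting bias is unknown.

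**What to change.** 1. Have the central platform draw block sizes at random within each stratum, for example 4 and 6.
2. Replace the block-size wording in Section 3.2.1 with a statement that permuted blocks of varying size are used. Hold the sizes in a restricted randomisation document, out of the protocol and all site documents.
3. In Section 3.4.1, change equal arm numbers per site and type to approximately equal. This is warranted in any case: a stratum that stops mid-block can already differ by 2, and one with an odd number of patients cannot be equal.

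The cost is a setting in the randomisation module and two edited sentences. The statistical price is that the maximum arm imbalance in a stratum rises from 2 to 3. The gain is a fall in allocations known with certainty from about 32% to about 6%; the best-guess rate improves only slightly, to about 68%.

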3.2.2 Primary and secondary endpoints

The **primary study outcome** will be the days lost (%) due to unplanned cardiovascular hospitalisations or allcause death, comparing remote patient monitoring and interventions (RPMI) group with remote patient monitoring and usual care (RPMUC) group only during the individual follow-up time.

As additional measure of this primary outcome we will report the freedom from the combined occurrence of death or unplanned hospitalisation/ambulatory administration of intravenous (IV) diuretics, IV antibiotics, or intravenous (IV) steroids.

The secondary end-points include:

a. All-cause mortality during the individual follow-up time (to a maximum of 575 days, i.e., the 547 days of the patient monitoring period plus 28 days from the final study visit)

b. Cardiovascular mortality during the individual follow-up time (to a maximum of 575 days, i.e., the 574 days

¹ A delay of 5+ months was encountered in the completion of the present document D8.2, in relation to the study protocol and the evaluation framework. This delay inevitably affects the progress of the next project phases and will eventually result in a time shift for platform completion. At the time of submission of the present deliverable, the estimated minimum shift is ~3 months, therefore the onset of the trial study is shifted from the originally planned M19 to M22, and will end at M48 instead of 45, at the earliest. Accordingly, all trial internal phases are shifting as well, following the new estimated plan.

- of the patient monitoring period plus 28 days from the final study visit)
- c. Time to first unplanned HF hospitalisation
- d. Time to first unplanned cardiovascular hospitalisation
- e. Total unplanned HF hospitalisations (recurrent event analysis)
- f. Total unplanned cardiovascular hospitalisations (recurrent event analysis)
- g. Days (%) lost due to HF hospitalisations during the individual follow-up time.
- h. Number of smart device alarm notifications.

i. Change in the Kansas City Cardiomyopathy Questionnaire score between baseline (i.e., when a patient enters the study) and month 18.

j. Change in the levels of N-terminal pro-B-type natriuretic peptide (NT-proBNP) between baseline and month 18.

k. Change in the Depression Score Patient Health Questionnaire 9 (PHQ-9) score between baseline and month 18.

I. Change in the Heart Failure Caregiver Questionnaire (HF-CQ version 5.0) between baseline and month 18.

- m. Rejection needing treatment in HT
- n. Driveline infection needing antibiotic in LVAD patients
- o. Unplanned visit for HF requiring intravenous (IV) Diuretic

p. Number of visits outside the protocol

Measurements for the primary endpoint and secondary outcomes will be collected upon registration, at every clinic visit and at the end of the study.

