- Demographic, clinical, and device data, and treatment results will be summarised using descriptive summary statistics. Data collected in the trial will be summarised overall and by treatment groups. Continuous variables will be presented with the numbers of observations, means, standard deviations, minimums, and maximums. For comparisons, the difference between the groups will be summarised with the difference of the two means together with 95% confidence intervals and tested using the two-sample t-test. These calculations will be done under the assumption that the data for the two groups are independent and approximately gaussian in distribution. If asymptotic assumptions fail, nonparametric summary statistics (medians, 25th and 75th percentiles) may be displayed. In addition, more appropriate non-parametric tests will be considered if the assumptions for the parametric tests are violated. For the comparison of two independent samples, if the data are not normally distributed, Mann-Whitney rank sum test will be performed instead of the parametric t-test,
- For categorical variables results will be summarised with subject counts, percentages. The differences between the two treatment groups will be summarised with the difference in percent and compared using the chi-square test or Fisher's exact test as appropriate.
- Survival analysis techniques will be used to analyse the time-to-event variables.

The primary analyses will compare the days lost due to unplanned cardiovascular hospitalisations or all-cause death and the survival free from death or unplanned hospitalisation/ambulatory administration of intravenous therapy between interventions group and usual care group by the means of the parametric t-test or non-parametric rank sum test as mentioned above.

To evaluate the additional measure of the primary outcome, the survival free from the combined endpoint, survival curves will be constructed using Kaplan-Meier estimates. Log-rank test results will also be computed for comparison of survival distributions between intervention and usual care groups.

Pre-specified subgroup analyses include:

- The three patient categories (HF, LVAD and HT)
- Males and Females
- Patients with a hospitalisation less than three months from the enrolment

• Patients older than 60 years

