- Cardiac Resynchronisation Therapy, with defibrillator (CRT-D) or without defibrillator (CRT-P)
- Aortic Aneurysm
- Heart Transplant
- LVAD Implant
- HF & CV medical therapies (ACEI/ARNI/ARB, BB, MRA, SGLT2i, diuretic, anticoagulant, antiplatelet, statin, amiodarone

Non-cardiovascular history

- Smoker [never, current, past (meaning >6 months)]
- Severe alcohol intake [never, current, past (meaning >6 months)]
- Thyroid disease (if yes, define hyper- or hypo-thyroidism)
- Cancer
- Anaemia
- Chronic Obstructive Pulmonary Disease (COPD)
- Chronic Kidney Disease
- Benign Prostatic hyperplasia
- Other than HF & CV medical therapies
- Recent HF hospitalisation discharge date, or recent urgent ED visit due to HF date
- Number of HF hospitalisations within the last 12 months
- Caregiver data (if caregiver available):
- Sex
- Date of birth, age
- Children (yes/no)
- Living situation (Living alone /Living with the person that cares for only /Living with the person cared for and other family members/ Other)
- Highest level of education (Up to and including high school/ Above high school education/ Other)
- Employment status (Working (full or part time) /Not currently working / Full-time homemaker / Retired /Student or other)
- Caregiver condition (Cardiovascular Disease/ Hypertension/Diabetes mellitus/ High cholesterol)

Data collected at every clinic visit (upon registration and at months 4,8,12 and 18):

- Weight
- Vital signs: Blood pressure, heart rate, Peripheral capillary oxygen saturation, Temperature
- ECG
- Rhythm
- Heart rate
- Conduction delay(LBBB,RBBB, LAH, LPH, incomplete RBBB or LBBB)
- QRS duration
- QTc
- PQ/PR
- Blood tests at months 4,8,12 (Urea, Creatinine, Potassium, Sodium, SGOT, SGPT, LDH, INR, CPK, Troponin, Uric Acid, CRP, White blood cells, Haemoglobin, Platelets and NT-proBNP)
- Blood tests at months 0(registration) and 18(Urea, Creatinine, Potassium, Sodium, SGOT, SGPT, LDH, INR, CPK, Troponin, Uric Acid, CRP, White blood cells, Haemoglobin, Platelets and NT-proBNP, Glucose, Magnesium, Cholesterol, Triglycerides, HDL, LDL, γGT, ALP, Total proteins, Albumin, Total Bilirubin, D-Dimers, Fibrinogen, Calcium, Phosphorus, CRP, Procalcitonin, TSH, FT3, FT4, B12, Fe, Ferritin)
- Depression score PHQ-9
- Kansas City Cardiomyopathy Questionnaire (KCCQ)
- Six-minute walk test
- Cardio-pulmonary exercise testing (upon registration and at month 18)

- VE/VCO2
- VO2max
- RER
- Echocardiography (upon registration and at months 8 and 18)

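### The stated test for change in KCCQ, NT-proBNP, PHQ-9 and HF-CQ makes no covariate adjustment for baseline or strata and, for the first three, leaves the month 4, 8 and 12 values unused

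*Protocol*

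**What the plan says.** Protocol Section 3.2.2, items i to l, defines four endpoints as change over the whole monitoring period:

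- KCCQ: "Change in the Kansas City Cardiomyopathy Questionnaire score between baseline (i.e., when a patient enters the study) and month 18"
- NT-proBNP: "Change in the levels of N-terminal pro-B-type natriuretic peptide (NT-proBNP) between baseline and month 18"
- PHQ-9: "Change in the Depression Score Patient Health Questionnaire 9 (PHQ-9) score between baseline and month 18"
- Caregiver questionnaire: "Change in the Heart Failure Caregiver Questionnaire (HF-CQ version 5.0) between baseline and month 18"

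Section 3.5 sets one general rule for comparing continuous variables. The group difference is "summarised with the difference of the two means together with 95% confidence intervals and tested using the two-sample t-test". The fallback is: "if the data are not normally distributed, Mann-Whitney rank sum test will be performed instead of the parametric t-test". No covariate, stratification factor or repeated-measures model is named.

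Section 3.7.3 lists KCCQ and PHQ-9 under "Data collected at every clinic visit (upon registration and at months 4,8,12 and 18". NT-proBNP is in the blood panel for months 4, 8 and 12 and in the panel for registration and month 18. Table 2 agrees. HF-CQ is scheduled at baseline and month 18 only, in both Section 3.7.3 and Table 2. The closing sentence of Section 3.2.2, which places secondary measurements at every clinic visit, is more general and does not fit that specific HF-CQ schedule.

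Section 3.2.1 stratifies randomisation by centre and patient type.

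**The concern.** Quality of life is part of the study aim in Section 3.2.1, and KCCQ is its direct measure. Read together, Sections 3.2.2 and 3.5 give an unadjusted comparison of change at a single time point. Information that the trial will already hold is left out in three ways:

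1. Baseline enters only by subtraction. The fitted relation between baseline and month 18 is not used.
2. Centre and patient type, which structure the randomisation and divide the sample into 200 heart failure, 150 LVAD and 100 transplant patients, are not in the comparison.
3. For KCCQ, PHQ-9 and NT-proBNP, three scheduled interim visits do not contribute. A patient with values at months 4, 8 and 12 but not at month 18 has no change score and leaves the comparison.

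At stake are wider intervals than necessary, some sensitivity to chance baseline imbalance, and a comparison confined to patients seen at month 18.

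**Working it through.** **The plan's own figure.** Section 3.5 gives 199 per arm for the primary endpoint: difference 29 − 17 = 12 days, SD 48, one-sided α 0.05, power 80%. It reproduces: 198 by the normal approximation, and 198.5, rounded up to 199, by the t-based calculation. It does not bear on the four change endpoints, for which no power is claimed. Below, 199 per arm serves only as a reference size.

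**Inputs.** The documents give no correlation ρ between baseline and month 18, so 0.3 to 0.8 is assumed. Equal SDs at both visits are assumed first, then relaxed.

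**Formulas**, per patient, in units of the squared month-18 SD, with equal SDs:

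- change score: 2(1 − ρ)
- ANCOVA: 1 − ρ²
- ratio: (1 − ρ²) / [2(1 − ρ)] = (1 + ρ)/2
- detectable difference at 80% power, two-sided 0.05: (1.96 + 0.84) × √variance × √(2/199)

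| ρ (assumed) | Var change | Var ANCOVA | Ratio | Detectable difference, change → ANCOVA (SD units) | ANCOVA power where change score has 80% | n per arm under ANCOVA for the same precision |
|---|---|---|---|---|---|---|
| 0.3 | 1.40 | 0.91 | 0.65 | 0.332 → 0.268 | 93.5% | 129 |
| 0.5 | 1.00 | 0.75 | 0.75 | 0.281 → 0.243 | 89.9% | 149 |
| 0.7 | 0.60 | 0.51 | 0.85 | 0.218 → 0.201 | 86.0% | 169 |
| 0.8 | 0.40 | 0.36 | 0.90 | 0.178 → 0.169 | 84.0% | 179 |

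**Unequal SDs.** Let the baseline SD be k times the month-18 SD. Then Var(change) = 1 + k² − 2kρ, and Var(change) − Var(ANCOVA) = (k − ρ)², which is never negative. The gain can still shrink. Section 3.4.2 requires PHQ-9 below 10 at entry, which may compress its baseline spread. With ρ = 0.5:

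- k = 0.7 (assumed): 1 + 0.49 − 0.70 = 0.79; ratio 0.75/0.79 = 0.95.
- k = 0.5 (assumed): 1 + 0.25 − 0.50 = 0.75; ratio 0.75/0.75 = 1.00, no gain.

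**Chance imbalance.** With equal SDs, a baseline difference d between arms separates the change-score estimate from the ANCOVA estimate by (1 − ρ)d. For d = 0.1 SD this is 0.07, 0.05, 0.03 and 0.02 SD at ρ = 0.3, 0.5, 0.7 and 0.8.

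**Missing month-18 values.** Section 3.5 expects about 10% attrition: 0.10 × 450 = about 45 patients. It does not say whether deaths are counted in that figure. Under Section 4.5 only data collected after withdrawal of consent are set aside, so earlier visits of patients who withdraw remain available. How many such patients will have interim values cannot be derived from the documents.

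**The case against.** The strongest reply is that Section 3.5 gives a general rule and ties a named test only to the primary outcome and its additional measure. It is not a full list of methods: Section 3.2.2 specifies recurrent-event analysis for two endpoints, which Section 3.5 never mentions. Models and missing-data rules for secondary endpoints are commonly left to a separate plan. This stands in part: the link from the t-test to these endpoints is by general rule, and the exclusion of patients without month 18 follows only if no missing-data rule is added. But the rule sits under the protocol's own analysis-plan heading and is the only method given for continuous variables, so the objection is to a stated choice.

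Several stronger readings are tempting, and the documents do not support them:

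- A reader might infer that baseline is ignored. It is subtracted; what is missing is its use as a covariate.
- A reader might infer that interim data are wasted for all four endpoints. HF-CQ has none.
- A reader might infer bias. With complete data, the change-score comparison is unbiased over repeated randomisation.
- A reader might infer that a few extreme NT-proBNP values will drive the result. The rank-sum fallback largely limits that for the test, although it is equally unadjusted and no effect estimate is stated with it.
- A reader might treat 45 lost patients as a minimum. Section 3.5 gives an approximate rate, not a floor.
- A reader might expect a mixed model to deal with deaths. It does not: it implicitly extrapolates values after death. ANCOVA for HF-CQ is equally limited to those with a month-18 value.

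**Conclusion.** The point holds as an avoidable loss of efficiency in four secondary endpoints. It is not an error that invalidates them, and it does not touch the primary endpoint. Under equal SDs and an assumed correlation of 0.3 to 0.8, the unadjusted change score has about 1.1 to 1.5 times the ANCOVA variance (1/0.90 to 1/0.65), a loss of 4 to 13.5 power points against an 80% reference. For PHQ-9 the gain could be about 5% or nil if the baseline spread is compressed. In large samples, ANCOVA is not less precise than the change score. The added value of centre and patient type depends on how strongly they predict outcome, for which the documents give no figure. The second part of the loss, the exclusion of patients without a month-18 value, is of the order of the expected 10% attrition.

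**What to change.** State these analyses before any comparison by arm:

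- **HF-CQ:** ANCOVA on the month-18 value with baseline, arm, centre and patient type.
- **KCCQ, PHQ-9 and log-transformed NT-proBNP:** a repeated-measures mixed model over months 4, 8, 12 and 18 with baseline value, visit, arm, arm-by-visit, centre and patient type. Report the adjusted month-18 difference with its confidence interval, back-transformed to a ratio for NT-proBNP.
- **Deaths:** present these results beside deaths by arm, already collected for secondary endpoint a, and state that the model does not resolve truncation by death.
- **Schedule wording:** align the closing sentence of Section 3.2.2 with the HF-CQ schedule in Section 3.7.3 and Table 2.

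The endpoints and visits stay as they are and no new data are needed. The cost is analysis wording, programming, and reliance on a missing-at-random assumption in the mixed model, which should be stated openly.
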